3.6.1 Treatment Definitions

For visit-based Safety data (ie, laboratory values, vital signs, ECGs, etc) data will be summarized by treatment (LEM5, LEM10) and duration of exposure to treatment (3, 6, 9 and 12 months). Treatment groups are LEM5 and LEM10, and include both (a) LEM Period 1 subjects on the On-Treatment Safety Analysis Set using the change from Study Baseline and (b) LEM Period 2 subjects previously receiving PBO on the On-Treatment Safety Analysis Set using the change from Period 2 Baseline. Summaries of exposure, AEs, TEMAV, clinically abnormal vital sign and ECG values will be summarized for:

- Period 1 data, where treatment groups are PBO, LEM5 and LEM10 in the Safety Analysis Set (ie, subjects who received at least 1 dose of study drug in Treatment Period 1)

- 12-month LEM exposure, where treatment groups are LEM5 and LEM10 in the On-Treatment Safety Analysis Set (ie., subjects who received at least 1 dose of lemborexant), where data will be summarized by exposure to treatment (3, 6, 9 and 12 months)

3.6.2 Extent of Exposure

The extent of exposure (mean daily dose, cumulative dose, duration of exposure) to study drug will be summarized descriptively. Period 1 data with LEM5 or LEM10 will be summarized for: the number (percent) of subjects who completed 1 month (30 or more days), 3 months (90 or more days), and 6 months (180 or more days). 12-month exposure with LEM5 or LEM10 will be summarized for: the number (percent) of subjects who completed 3 months (90 or more days), 6 months (180 or more days), 9 months (270 or more days) and 12 months (365 or more days) of dosing.

The duration of exposure to study drug is defined as the date of last dose – the date of first dose date +1.

The exposure to Run-In Period placebo will be presented in the subject data listings only.

3.6.3 Adverse Events

The AE verbatim descriptions (investigator terms from the eCRF) will be classified into standardized medical terminology using the MedDRA. Adverse events will be coded to the MedDRA (Version 17.0 or higher) lower level term closest to the verbatim term. The linked MedDRA PT and primary system organ class (SOC) are also captured in the database.

Only those AEs that are treatment-emergent will be included in summary tables. All AEs, treatment-emergent or otherwise, will be presented in subject data listings. AEs will be classified as TEAEs up to 14 days after the last study treatment (see below).

A TEAE is defined as an AE that emerges during treatment (including the Run-In period up to 14 days after the last dose of study drug from the first dose of study drug), having been absent before the randomized study medication is started or

- Reemerges during active treatment, having been present at pretreatment (before the randomized study medication is started) but stopped before treatment, or
- Worsens in severity during active treatment (after randomized study medication starts) relative to the pretreatment state, when the AE is continuous.

Separately, a TEAE during each Period (ie, Run-In, Treatment Period 1 or Treatment Period 2) is defined as:

1. TEAE during the Run-In: AE that emerges prior to the date of first dose in Treatment Period 1 or the date of last dose in Run-In + 14 days, whichever comes earlier.
2. TEAE during Period 1: AE that emerges after the date of first dose in Treatment Period 1 but prior to (a) the date of first dose in Period 2 or (b) the date of last dose in Treatment Period 1 + 14 days, whichever comes earlier.
3. TEAE during Period 2: AE that emerges after the date of first dose in Treatment Period 2 but prior to the date of last dose in Treatment Period 2 + 14 days, whichever comes earlier.

Adverse events will be summarized using the Safety Analysis Set and On-Treatment Safety Analysis Set by treatment groups.

The number (percentage) of subjects with TEAEs during the Run-In Period will be summarized by SOC and PT.

The following summary tables will be produced for the Period 1 (Safety Analysis Set) and On-Treatment (On-Treatment Safety Analysis Set) separately.

An overview table of TEAEs, including number of subjects with TEAEs, treatment-emergent serious adverse events (SAEs), deaths, severe TEAEs, study drug related TEAEs, TEAEs leading to study drug withdrawal will be provided for each treatment group.

In addition, the following summaries will be produced for the TEAEs by treatment group:

- Incidence of TEAEs by PT in descending order
- Incidence of TEAEs by SOC and PT
- Incidence of treatment-related TEAEs by SOC and PT
- Incidence of TEAEs by SOC, PT, and maximum severity
- Incidence of treatment-related TEAEs by SOC, PT, and maximum severity
- Incidence of TEAEs by SOC, PT, and relationship to treatment

If a subject experiences more than one TEAE within a preferred term, the subject will be counted only once in the calculation of incidence of TEAE within that preferred term. Similarly, if a subject experiences more than one TEAE within a SOC, the subject will be counted only once in the calculation of incidence of TEAE within that SOC. If a subject experiences more than one TEAE within a preferred term (or SOC), the occurrence with the highest severity will be used in the calculation of the incidence of TEAE within that preferred term (SOC) by severity. If a subject experiences more than one TEAE within a preferred term (or SOC), the occurrence considered most closely related to study drug will be used in the calculation of the incidence of TEAE with that preferred term (SOC) by relationship (given by investigator).

The following summaries will also be presented for the treatment-emergent SAEs:

- Incidence of treatment-emergent SAEs by SOC and PT

- Incidence of treatment-emergent SAEs by SOC, PT, and relationship to treatment.

In addition, number and percentage of subjects with TEAEs and treatment-related TEAEs leading to discontinuation from study treatment will also be summarized by MedDRA SOC, PT for each treatment group.

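### The period rules in SAP 3.6.3 leave an adverse event with onset on the first-dose date in no period, so it drops out of the placebo-controlled TEAE tables (minor)

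*SAP*

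**What the plan says.** SAP 3.6.3 first gives a general TEAE definition that runs from the first dose of study drug, Run-In included, and says "AEs will be classified as TEAEs up to 14 days after the last study treatment". It then gives three period rules:

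- **Rule 1, Run-In:** "TEAE during the Run-In: AE that emerges prior to the date of first dose in Treatment Period 1", or before the last Run-In dose plus 14 days if that is earlier.
- **Rule 2, Period 1:** "TEAE during Period 1: AE that emerges after the date of first dose in Treatment Period 1 but prior to" the earlier of "a) the date of first dose in Period 2 or (b) the date of last dose in Treatment Period 1 + 14 days, whichever comes earlier".
- **Rule 3, Period 2:** "TEAE during Period 2: AE that emerges after the date of first dose in Treatment Period 2 but prior to the date of last dose", with 14 days added to that last date.

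The same section restricts summary tables to TEAEs and puts all other events in listings only. It calls for a Run-In table, a set of Period 1 tables on the Safety Analysis Set, and a set of On-Treatment tables on the On-Treatment Safety Analysis Set. It lists no table for Period 2 alone and does not say which definition feeds the On-Treatment tables.

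Protocol 9.7.1.8.2 has its own Period 2 definition for former-placebo subjects in the 12-month exposure analysis. It asks whether the event arose in Period 2 and was absent before Period 2 treatment, and it sets no strict date bound.

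**The concern.** Each boundary between periods is written with strict inequalities on both sides, so the boundary date itself falls through. That date is the day on which a subject first takes randomized drug or, for a former-placebo subject at the second boundary, first takes lemborexant.

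The SAP treats that day differently elsewhere. SAP 3.6.2 adds one to the date difference when computing duration of exposure, so the first-dose date counts as an exposed day. SAP 3.2.5 uses inclusive wording for concomitant medications. Programmed as written, Day 1 would add to exposure while its events were excluded from the table.

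The Period 1 tables are the only placebo-controlled adverse event comparison (SAP 3.6.1). They include the summaries of cataplexy, potential cataplexy, falls and seizures in SAP 3.6.3.1. Where counts are low, losing a single event can be visible. A reaction confined to the first evening would not be recovered by a later onset in the same subject.

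**Working it through.** This is a logic check; the plan states no figure to reproduce.

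**Inputs.** The three rules come from SAP 3.6.3. The dates are illustrative assumptions: last Run-In dose on the day before Day 1, first Period 1 dose on Day 1, last Period 1 dose on Day 180, first Period 2 dose on Day 181, last Period 2 dose on Day 364.

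**Rules as inequalities on onset date d, with the day before Day 1 coded as 0.**

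- Run-In: d < min(1, 0 + 14) = 1
- Period 1: d > 1 and d < min(181, 180 + 14) = 181
- Period 2: d > 181 and d < 364 + 14 = 378

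**Result for each onset date.**

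| Onset | As written | With inclusive starts in rules 2 and 3 |
|---|---|---|
| Day before Day 1 | Run-In | Run-In |
| Day 1 | none | Period 1 |
| Days 2 to 180 | Period 1 | Period 1 |
| Day 181 | none | Period 2 |
| Days 182 to 377 | Period 2 | Period 2 |
| Day 378 (last dose + 14) | none | none |

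The 14-day alternatives only cap a period from above, so they rescue neither first-dose date. The Period 2 first-dose date stayed unassigned with 1, 5, 13, 14 and 20 days between the last Period 1 dose and the first Period 2 dose. With inclusive starts no onset date falls in two periods. Day 378 then remains because the 14-day limit is strict, although the general sentence in the same section runs up to 14 days.

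**How much of the first-dose date is post-dose.** Drug is taken within 5 minutes before bedtime (protocol 9.2.3 and 9.4.8), and eligible bedtimes run from 21:00 to 01:00 (protocol 9.3.1, criteria 5 and 12).

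- Dose before midnight: at most about 24:00 − 21:00 = 3 hours after the dose carry the first-dose date. Events after midnight or next morning fall on the following date and are counted.
- Dose after midnight: the whole first night and the next morning share the first-dose date and are lost.

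The documents give no adverse event onset data, so these hours cannot be turned into a number of events.

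**The case against.** The strongest reply is that the practical effect is slight. Most first doses may come before midnight, with the subject then in bed. Next-morning sleepiness, the residual effect discussed in protocol 7.2 and 9.4.4, then falls on Day 2 and is counted. Tables 9 and 10 of the SAP also open their first post-baseline windows at day 2. Day 1 includes the baseline clinic visit, with blood sampling and an ECG (protocol 9.1.1.3), so a date-only inclusive rule would admit some pre-dose events. Derivation rules sit in separate documents (SAP 7) and may already handle the boundary. All of this bears on size, and it stands. It does not change what the SAP text says.

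A reader might infer more than the documents support:

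- **That events vanish from Period 2 tables.** SAP 3.6.3 lists no Period 2-only adverse event table. Subjects already on lemborexant continue the same dose, so for them that date is not a first exposure. For former-placebo subjects, protocol 9.7.1.8.2 supplies a definition without the gap.
- **That about 1/180 = 0.6% of Period 1 events are lost, or several percent with clustering after the first dose.** The first figure assumes uniform onset and counts the whole calendar day, including the hours before the dose. On the same assumption, 3 post-dose hours would be (3/24)/180, about 0.07%. No source in the documents supports a higher range.
- **That Run-In events can never qualify.** The general definition does include the Run-In while requiring the event to be absent before randomized drug ("having been absent before the randomized study medication is started or"). But rule 1 defines Run-In TEAEs separately and a Run-In table is specified, so no effect on a table is shown.

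**Conclusion.** The point holds as a boundary error of minor severity. Read literally, rules 1 and 2 place an event with onset on the Period 1 first-dose date in no period, and it is left out of the Period 1 tables. It remains a TEAE under the general definition, provided it began after the dose and was not present before, and it remains in the listings. The gap at the Period 2 first-dose date affects reported results only if rule 3 defines events for former-placebo subjects in the On-Treatment tables, which the SAP leaves open. The loss of day 14 contradicts the general sentence in the same section.

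The loss is probably small and cannot be quantified from the documents. This conclusion assumes that the Period 1 tables are built from rule 2 as written and that the separate programming specifications do not override it.

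**What to change.** In SAP 3.6.3:

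1. In rules 2 and 3, start each period *on or after* the date of first dose. Where onset time is recorded, use it to set aside Day 1 events that began before the dose.
2. Make the 14-day limit inclusive: *on or before* last dose + 14 days. Keep the limit at the next period's first dose strict, so that no date falls in two periods.
3. State that former-placebo subjects in the On-Treatment tables follow the Period 2 definition in protocol 9.7.1.8.2.

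The cost is a wording change and a few comparison operators in the derivation; no new data are needed. The downside is small: where onset time is missing, some pre-dose Day 1 events will count as Period 1 TEAEs. Because they precede randomized treatment, this should fall equally across the arms.

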9.5.1.5.1 ADVERSE EVENTS AND EVENTS ASSOCIATED WITH SPECIAL SITUATIONS

An AE is any untoward medical occurrence in a patient or clinical investigation subject administered an investigational product. An AE does not necessarily have a causal relationship with the medicinal product. For this study, the study drug(s) is lemborexant.

The criteria for identifying AEs in this study are:

- Any unfavorable and unintended sign (including an abnormal laboratory finding), symptom, or disease temporally associated with the use of an investigational product, whether or not considered related to the investigational product (Note: Every sign or symptom should not be listed as a separate AE if the applicable disease [diagnosis] is being reported as an AE)
- Any new disease or exacerbation of an existing disease
- Any deterioration in nonprotocol-required measurements of a laboratory value or other clinical test (eg, ECG or x-ray) that results in symptoms, a change in treatment, or discontinuation of study drug
- Recurrence of an intermittent medical condition (eg, headache) not present pretreatment (Baseline)

An abnormal laboratory test result should be considered an AE if the identified laboratory abnormality leads to any type of intervention, withdrawal of study drug, or withholding of study drug, whether prescribed in the protocol or not.

All AEs observed during the study will be reported on the CRF. All AEs, regardless of relationship to study drug or procedure, should be collected beginning from the time the subject signs the study ICF through the last visit. SAEs will be collected for 28 days after the last dose.

Abnormal laboratory values should not be listed as separate AEs if they are considered to be part of the clinical syndrome that is being reported as an AE. It is the responsibility of the investigator to review all laboratory findings in all subjects and determine if they constitute an AE. Medical and scientific judgment should be exercised in deciding whether an isolated laboratory abnormality should be classified as an AE. Any laboratory abnormality considered to constitute an AE should be reported on the Adverse Event CRF.

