9.7.1.8.2 ADVERSE EVENTS

The AE verbatim descriptions (investigator terms from the CRF) will be classified into standardized medical terminology using the MedDRA. Adverse events will be coded to the MedDRA (Version 17.0 or higher) lower level term (LLT) closest to the verbatim term. The linked MedDRA preferred term (PT) and primary system organ class (SOC) are also captured in the database.

A TEAE is defined as an AE that emerges during treatment (including the Run-In Period), having been absent at pretreatment (before the Run-In Period) or

- Reemerges during treatment, having been present at pretreatment (before the Run-In Period) but stopped before treatment, or
- Worsens in severity during treatment relative to the pretreatment state, when the AE is continuous.

Separately, for 12-month exposure analysis, LEM Period 2 subjects previously receiving PBO on the On-Treatment Safety Analysis Set will have a separate definition for TEAE in Period 2, where an AE is defined as (revised per Amendment 06):

- Emerges during Period 2 having been absent prior to Period 2 treatment, or
- Reemerges during treatment, having been present prior to Period 2 treatment but stopped before Period 2 treatment, or
- Worsens in severity during Period 2 treatment relative to the pre Period 2 state, when the AE is continuous.

Only those AEs that are treatment-emergent will be included in summary tables. All AEs, treatment-emergent or otherwise, will be presented in subject data listings. AEs will be classified as TEAEs up to 14 days after the last study treatment.

Adverse events will be summarized using the Safety Analysis Set and, where appropriate, the On-Treatment Safety Analysis Set. The TEAEs will be summarized by treatment group at the start of the TEAE. The incidence of TEAEs will be reported as the number (percentage) of subjects with TEAEs by SOC and PT. A subject will be counted only once within an SOC and PT, even if the subject experienced more than 1 TEAE within a specific SOC and PT. The number (percentage) of subjects with TEAEs during the Run-In Period, and after the Run-In Period will be summarized separately. The number (percentage) of subjects with TEAEs during the Period 1 (Safety Analysis Set) and 12-month LEM exposure (On-Treatment Safety Analysis Set) will also be summarized separately. (revised per Amendment 06)

All the following summaries will be repeated for Period 1 and 12-month LEM exposure. (revised per Amendment 06)

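### The SAP's Period 2 TEAE rule omits worsening relative to the pre-Period 2 state, which the protocol counts for placebo subjects switched to lemborexant

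*SAP*

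**What the plan says.** Protocol 9.7.1.8.2 has a general TEAE definition and, since Amendment 06, a second one for subjects who took placebo in Period 1 and lemborexant in Period 2. The second applies to the 12-month exposure analysis. An event qualifies if it is new in Period 2, if it had stopped before Period 2 and returns, or if it meets this criterion: "Worsens in severity during Period 2 treatment relative to the pre Period 2 state, when the AE is continuous". The same section assigns each TEAE to the treatment group at the time the TEAE starts.

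SAP 3.6.3 also has a general definition, with new, returning and worsening events. Its worsening criterion reads "Worsens in severity during active treatment (after randomized study medication starts) relative to the pretreatment state, when the AE is continuous", and its re-emergence criterion uses the same reference point: "having been present at pretreatment (before the randomized study medication is started) but stopped before treatment, or". The SAP then adds period rules, introduced by "Separately, a TEAE during each Period (ie, Run-In, Treatment Period 1 or Treatment Period 2) is defined as". Item 3 reads "TEAE during Period 2: AE that emerges after the date of first dose in Treatment Period 2", with an upper limit of 14 days after the last Period 2 dose. Items 1 (Run-In) and 2 (Period 1) are built the same way, on emergence within a date range.

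Only treatment-emergent events enter the summary tables. These are produced separately for Period 1 and for the On-Treatment set, which includes the switched subjects.

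**The concern.** The protocol wrote a definition for exactly this cohort, and the SAP does not carry it over. For a switched subject, the natural reference for lemborexant safety is the state just before the first lemborexant dose. No SAP TEAE rule compares severity with that state.

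The tables at stake are the 12-month lemborexant exposure tables: overall TEAEs, severe TEAEs, serious TEAEs, TEAEs leading to withdrawal and maximum severity (SAP 3.6.3), and the selected events of SAP 3.6.3.1. Long-term safety over 12 months is a stated purpose of the study (Protocol 7.2). An event that appears or becomes severe only on lemborexant belongs in those tables. An event already present on placebo that lemborexant makes worse belongs there too, under the protocol's rule.

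**Working it through.** No plan figure needs to be reproduced. The check compares the two texts and then sizes the cohort.

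**Criteria for a Period 2 TEAE in a former-placebo subject**

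| Criterion | Protocol 9.7.1.8.2, Period 2 rule | SAP 3.6.3, item 3 | SAP 3.6.3, general definition |
|---|---|---|---|
| New event | Yes, absent before Period 2 | Yes, by date | Yes, absent before randomized drug |
| Returning event | Yes, stopped before Period 2 | Not stated | Yes, stopped before randomized drug |
| Worsening event | Yes, against the pre-Period 2 state | Not stated | Yes, against the state before randomized drug |

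**Worked cases**, each a placebo subject switched to lemborexant:

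1. An event starts mild in Period 1, continues, and becomes severe in Period 2. Under the protocol it is a Period 2 TEAE by worsening. Under SAP item 3 it is not, because it emerged before the first Period 2 dose. It stays a Period 1 placebo TEAE.
2. An event is present before randomization, continues, and worsens only in Period 2. Under the protocol it is a Period 2 TEAE. Under the SAP it meets the general worsening criterion, so it is a TEAE overall, but no SAP rule places it in Period 2 or on lemborexant.
3. An event occurs in Period 1, stops, and recurs in Period 2. Under the protocol it is a TEAE by re-emergence. Under SAP item 3 it is probably counted, because the recurrence has its own onset date and item 3 does not require earlier absence.

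So the loss is in cases 1 and 2, that is, worsening. Case 3 is mostly a matter of wording.

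**Choice or omission?** SAP section 1 cites a protocol dated 13 Aug 2018, the date of Amendment 06 in the protocol's revision history. SAP 3.6.1, 3.6.5 and 6.2.1 use a Period 2 Baseline for switched subjects' visit-based safety data. Neither SAP Table 1 nor SAP section 5 declares a change to the TEAE criteria; the Table 1 entry for 3.6.3 records only that the up-to-12-month and up-to-6-month treatment definitions were removed. This looks like an omission.

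**Size of the cohort.** Inputs are 300 subjects per group, hence 600 randomized to lemborexant, and 150 per group remaining at Month 6 under the plan's 50% discontinuation scenario (Protocol 9.7.2, SAP 2).

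- At 50% retention: 150 / (600 + 150) = 150/750 = 20%.
- At full retention: 300 / (600 + 300) = 300/900 = 33%.

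**The case against.** The strongest reply is that the period rules are only date windows for events that already meet the general definition. The SAP does not say so, and even on that reading nothing compares severity with the pre-Period 2 state, so case 1 is still not a lemborexant TEAE.

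A second reply is that worsening may be captured at data entry. Protocol 9.5.1.5.1 makes an exacerbation of an existing disease an AE criterion, and Protocol 9.5.1.2.1 says a worsening of recorded daytime sleepiness is reportable. These show that some worsening would be an AE in its own right. They do not settle how a severity increase within an ongoing AE is recorded. This reply stands in part.

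It also stands that safety analyses are descriptive with no hypothesis tests (SAP 3.6), and that every AE remains in the listings.

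A reader might infer more than the documents support:

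- That all worsening or returning events in switched subjects are lost. A recurrence with a new onset date meets item 3, and worsening entered as a new record would too.
- That events starting in Run-In and worsening on randomized drug drop out of the Period 1 tables, against the protocol. Item 2 says "TEAE during Period 1: AE that emerges after the date of first dose in Treatment Period 1", but the SAP's general worsening criterion covers such events with the right reference state, and the protocol has no separate Period 1 definition to contradict.
- That screening events count as Run-In TEAEs. Item 1 says "TEAE during the Run-In: AE that emerges prior to the date of first dose in Treatment Period 1" and gives no start date, and AEs "should be collected beginning from the time the subject signs the study ICF through the last visit". But the general definition starts from the first dose of study drug, and SAP 3.2.5 counts Run-In placebo as study drug. The point needs clarifying and does not touch lemborexant incidence.
- That 20% to 33% of events are lost. Those figures are shares of subjects.

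**Conclusion.** The point holds in this limited form: the SAP omits the protocol's rule that worsening relative to the pre-Period 2 state makes an event a Period 2 TEAE in former-placebo subjects. No other SAP rule credits lemborexant with an event that began on placebo and worsened after the switch. The 12-month exposure tables would then undercount lemborexant TEAEs in a cohort of 20% to 33% of exposed subjects. How many events this means cannot be estimated from the documents.

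The conclusion rests on two assumptions. First, item 3 governs switched subjects in the On-Treatment tables. The SAP does not say so outright, but item 3 is its only TEAE rule that dates events from the switch. Second, a severity increase within an ongoing AE does not open a new record. If it does, some or all of the gap closes. The SAP should be corrected, but no efficacy conclusion or hypothesis test is affected.

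**What to change.** In SAP 3.6.3:

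- For former-placebo subjects, replace item 3 with the protocol's definition: the event emerges in Period 2, re-emerges after stopping before Period 2, or worsens relative to the pre-Period 2 state. Keep the 14-day upper limit.
- State that this definition governs the AE tables for 12-month lemborexant exposure.
- State that an event qualifying by worsening is attributed to the subject's Period 2 lemborexant dose, and how the severity change is dated. Taking the worsening as the start of the TEAE keeps this consistent with the protocol's attribution rule.
- As a clarification only, state that items 1 and 2 are date windows applied to events meeting the general definition, with a worsened event dated at worsening.

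The cost is a few lines of text and a derivation flag, plus a check of the eCRF. Attribution by worsening needs a dated severity change, and the documents do not show that one is collected. If it is not, the SAP should say so and state how such events are handled.
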